group participants according to the treatment they actually receive.

Full Analysis Set

The FAS will consist of all randomised participants whether or not they experienced significant protocol deviations affecting evaluations.

they experienced significant protocol deviations affecting evaluation of the endpoints. All analyses using the FAS will group participants

according to the randomised treatment.

Modified Full Analysis Set (mFAS) The mFAS will consist of all randomised and eligible participants with confirmed intra-articular synovitis on baseline MRI in FAS (grouped according to randomised treatment). The mFAS applies analysis flags to censor data after certain intercurrent events:

Flag P: Censors data after discontinuation or interruption of treatment for unrelated reasons (i.e. due to logistical issues or AEs due to an unrelated medical condition not considered to be due to treatment or the underlying RA disease) and resulting in >20% reduction in treatment administered during the approximately 4-week period since last visit. If treatment is resumed following an interruption, then subsequent data may be included provided at least 80% of treatment is taken during the previous 4-week period. This will be particularly useful for targeting Estimands 1 and 4.

Flag A: Censors data after discontinuation or interruption of treatment for any reason or any increase in RA medications and will be particularly useful for targeting hypothetical estimands (Estimands 2A and 3A). Only interruptions resulting in >20% reduction in treatment administered during the approximately 4-week period since last visit are considered relevant; for shorter interruptions, all resulting data are selected. If treatment is resumed following an interruption, then subsequent data may be included provided at least 80% of treatment is taken during the previous 4-week period.

Flag B: Censors data after discontinuation of treatment for unrelated reasons or any increase in RA medications and will be particularly useful for targeting the 'partially' hypothetical estimands (Estimands 2B and 3B). Interruptions for unrelated reasons are handled in the same way as Flag P.

Pharmacokinetics (PK) Set

The PK set will consist of all participants who receive at least 1 dose of MBS2320 and have at least 1 evaluable PK concentration. Analyses using the PK population will group participants according to treatment received.

Statistical analysis will be performed using SAS software Version 9.4 or later. Continuous variables will be summarised using the mean, standard deviation, median, minimum value, and maximum value. Categorical variables will be summarised using frequency counts and percentages. Data will be listed in data listings.

Details of the statistical analyses, methods, and data conventions will be described in the statistical analysis plan (SAP). All statistical tests will be 2-sided and performed using a 5% significance level, leading to 95% (2-sided) confidence intervals (CIs), unless indicated otherwise.

Analysis of Primary Efficacy Endpoint

Main Estimation of Primary Efficacy Estimand 1

The primary efficacy estimand is the absolute difference between each of the 3 different doses of MBS2320 and placebo in the percentage of participants who would achieve successful composite clinical response at Week 12 (which assumes failure for those who have any increase in RA medications or treatment discontinuation due to lack of efficacy or tolerability issues). The primary efficacy estimand will be estimated using a logistic regression model and the delta method, with the stratification factors and treatment as factors using the mFAS (Flag P). Missing data will not be imputed and are assumed missing completely at random (MCAR).

Sensitivity Analysis of Primary Efficacy Estimand 1

In the sensitivity analysis of the primary efficacy estimand, multiple imputation (MI) assuming missingness at random (MAR) will be used to impute any missing component of the composite clinical response at Weeks 4, 8, and 12, and then to derive the composite

outcomes. The logistic model will be fitted to each multiply imputed data set and the estimates of difference in percentages and standard error (SE) from the delta method will be pooled using Rubin's method. The overall difference of each dose relative to placebo will be presented with *P* value.

Also, in order to further study the successful composite clinical response profile across active doses, an additional sensitivity analysis will be conducted for studying the dose response relationship among the 3 MBS2320 doses and placebo dose. A logistic model will be fitted to multiply imputed data sets with dose in mg as a continuous variable to assess the trend across dose, including placebo as zero dose (i.e. placebo=0 mg dose level and dose levels of 5 mg, 20 mg, and 40 mg). The slope with CI and *P* value will be pooled using Rubin's method.

Analysis of Key Secondary Efficacy Endpoints

Main Estimation of Secondary Efficacy Estimand 2A

The first key secondary efficacy estimand (Estimand 2A) is based on the difference in mean change in Rheumatoid Arthritis Magnetic Resonance Imaging Score (RAMRIS) score from baseline to Week 12, as though no increase in any other RA medication and no treatment discontinuation for any reason, in patients with MBS2320 (5 mg, 20 mg, or 40 mg once daily) compared to placebo.

All assessments after any of the intercurrent events will be censored. An MI model will be used to impute any missing (or censored) score at Week 12 assuming MAR. The RAMRIS score and change from baseline in RAMRIS score will be derived on each multiply imputed data set and analysed using analysis of covariance (ANCOVA) with fixed effect terms for treatment and stratification factors, and baseline RAMRIS score as covariate. Rubin's method will be used to pool results so that the differences in mean change in RAMRIS score can be presented with 95% CI and *P* value.

Estimation of Supportive Efficacy Estimand 2B

Estimand 2B is defined as the difference in mean change in RAMRIS score from baseline to Week 12 in patients with MBS2320 (5 mg, 20 mg, or 40 mg once daily) compared to

placebo, irrespective of treatment discontinuation or interruption due to tolerability issues or lack of efficacy and as though no increase in any other RA medication. Data after all intercurrent events except discontinuation or interruption of treatment due to tolerability issues or lack of efficacy will be censored. Data missing for reasons unrelated to treatment (e.g. participant not willing to undergo MRI scan) will be imputed under the MAR assumption.

A reference-based multiply imputation model will be used to impute missing data after discontinuation of treatment due to related reasons (tolerability issues or lack of efficacy). As for Estimand 2A, the change from baseline in RAMRIS score will be derived on each multiply imputed data set and analysed using ANCOVA, and Rubin's method will be used to pool results.

Main Estimation of Secondary Efficacy Estimand 3A

A mixed model for repeated measures (MMRM) will be fitted to change from baseline at Weeks 4, 8, and 12 as the dependent variable and including fixed effects for DAS28-hsCRP baseline covariate, treatment, visit, treatment by visit interaction, and the stratification factors. An unstructured covariance will be used to model the covariances over time on participants. The least squares mean change from baseline in DAS28-hsCRP and differences relative to placebo with 95% CI and *P* value will presented at each time point.

Missing data are assumed to be MAR in the MMRM, which is well suited to estimate this type of hypothetical estimand.

Main Estimation of Secondary Efficacy Estimand 3B

Similar estimation (via MMRM) as described for Estimand 3A will be conducted for Estimand 3B. Note that this requires participants who discontinue treatment to return at Week 12 for assessment. Missing data are assumed to be MAR, which is unlikely to hold in the case of dropouts following discontinuation of treatment.

A sensitivity analysis will be conducted for Estimand 3B, using a reference-based MI model to impute missing data after discontinuation due to related reasons. The change from baseline

in DAS28-hsCRP will be derived on each multiply imputed data set and analysed using MMRM, and Rubin's method will be used to pool results.

Main Estimation of Secondary Efficacy Estimand 4

The estimation of Estimand 4 is similar to that described for Estimand 1. A logistic model will be fitted to successful composite clinical response at each of Weeks 4 and 8 including the stratification factors and treatment (qualitative) as factors; missing data will not be imputed and assumed MCAR.

In a sensitivity analysis, an MI model will be used to impute any missing components of the composite clinical response at Weeks 4, 8, and 12. Logistic model will be fitted to each multiply imputed data set and Rubin's method use to pool results. The overall difference of each dose relative to placebo will be presented with *P* value, at each time point.

Additional sensitivity analysis of the successful composite clinical response at Weeks 4, 8, and 12 will be performed using Logistic Generalized Linear Mixed Model with fixed effects for treatment, visit, treatment by visit interaction, and the stratification factors. More details will be provided in the SAP.

Analyses of Other Efficacy and Exploratory Endpoints

The other efficacy endpoints will be analysed descriptively, based on the mFAS (Flag B), except for ordinal endpoints (e.g. ACR50 & ACR70) which will be analysed based on mFAS (Flag P). Sensitivity analysis may be undertaken; details will be provided in the SAP.

The exploratory efficacy endpoints will be analysed descriptively, based on the mFAS (with no flags applied) and the mFAS (Flag A). Sensitivity analysis may be undertaken; details will be provided in the SAP.

Analysis of Pharmacokinetic Endpoints

MBS2320 and MBS2473 plasma concentrations will be determined in pre-dose samples at Weeks 4 and 12, postdose samples collected 3 (± 1) hours following last dose at Week 12, and at EOS.

Plasma concentration of MBS2320 and MBS2473 (where applicable) will be determined for each sample, excluding placebo controls.

All MBS2320 and MBS2473 plasma concentration data will be listed by participant and visit/sampling time point and summarised by administered treatment.

SAS® software Version 9.4 or higher (SAS Institute, Inc, Cary, North Carolina) will be utilised for the generation of any tables, listings, and figures.

Analyses of Safety

The incidence of treatment-emergent AEs for the safety population will be summarised by treatment group. Adverse events will be coded using the Medical Dictionary for Regulatory Activities to classify events under primary system organ class and preferred term. Adverse event data will be presented in incidence tables. Adverse events will also be summarised by severity, seriousness, and relationship to IP for each treatment group. Data will also be listed in data listings.

The incidence of laboratory abnormalities by type, frequency, and severity will be summarised by treatment groups. Change from baseline in continuous laboratory variables will be summarised by visit and treatment groups.

All other safety variables (including vital signs and ECGs) will be summarised by treatment group and visit.

Other Analyses

Summary statistical analyses will be provided for demographics, medical history, and physical examination, and ophthalmological assessments at baseline.

Version and Date of Protocol: Version 2.0, 12 January 2023

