- 1. Change in exploratory biomarkers (which may include but will not be limited to: inflammatory cytokines, metabolites, and biomarkers of bone turnover) compared to baseline at Week 12;
- 2. Change in peripheral blood leucocyte phenotype (which may include but will not be limited to: flow cytometry, gene expression, and/or protein levels) compared to baseline at Weeks 4 and 12;
- 3. Change in ACPA levels from screening to Week 12;
- 4. Change in rheumatoid factor compared to baseline at Week 12.

Other exploratory endpoints will be defined in the SAP.

ACPA=anti-citrullinated protein antibody; ACR20=American College of Rheumatology 20% response; ACR50=American College of Rheumatology 50% response; ACR70=American College of Rheumatology 70% response; CARLOS=cartilage loss; CDAI=clinical disease activity index; DAS28=disease activity score 28 joints; EOS=end of study; EQ-5D=EuroQoL-5 dimensions; EULAR=European League Against Rheumatism; FACIT-F=Functional Assessment of Chronic Illness Therapy-Fatigue; HAQ-DI=Health Assessment Questionnaire-Disability Index; hsCRP=high-sensitivity C-reactive protein; MRI=magnetic resonance imaging; MTX=methotrexate; RA=rheumatoid arthritis; RAID=Rheumatoid Arthritis Impact of Disease; RAMRIS=rheumatoid arthritis MRI scoring system; SAP=statistical analysis plan; SDAI=simplified disease activity index; SJC=swollen joint count; TEAE=treatment-emergent adverse event; TJC=tender joint count; VAS=visual analogue scale.

Diagnosis and Main Criteria for Inclusion and Exclusion:

Inclusion Criteria

Each participant must meet all the following criteria to be enrolled in this study:

- 1. Between 18 and 75 years of age, inclusive.
- 2. Diagnosed with RA based on either the 1987-revised American College of Rheumatology (ACR) classification criteria or the 2010 ACR/ European League Against Rheumatism (EULAR) criteria for ≥3 months prior to screening.
- 3. Has active RA as defined by the following minimum disease activity criteria:
 - ≥6 swollen joints (based on 66 joint counts) at screening and baseline visits.
 - ≥6 tender joints (based on 68 joint counts) at screening and baseline visits.
 - High-sensitivity C-reactive protein (hsCRP) > upper limit of normal reference range (ULN) at screening. One repeat assessment is acceptable for C-reactive protein per Investigator's discretion if all other eligibility criteria are met.

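### Pre-specifying baseline DAS28-hsCRP in the Estimand 1 and 4 logistic models would cost almost nothing and could give a modest, uncertain gain in precision

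*Combined protocol and SAP*

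**What the plan says.** All references are to the Statistical Methods part of the Protocol Synopsis in the combined protocol and SAP.

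- **Estimand 1 (primary).** The target is a risk difference: "The primary efficacy estimand is the absolute difference between each of the 3 different doses of MBS2320 and placebo" in the percentage with composite response at Week 12. It is to be "estimated using a logistic regression model and the delta method, with the stratification factors and treatment as factors using the mFAS (Flag P".
- **Estimand 4 (Weeks 4 and 8).** A logistic model is fitted at each visit, "including the stratification factors and treatment (qualitative) as factors; missing data will not be imputed and assumed MCAR".
- **Additional repeated-measures sensitivity analysis.** This is a "Logistic Generalized Linear Mixed Model with fixed effects for treatment, visit, treatment by visit interaction, and the stratification factors".
- **Estimand 2A (MRI).** The ANCOVA has "fixed effect terms for treatment and stratification factors, and baseline RAMRIS score as covariate".
- **Estimand 3A (DAS28-hsCRP).** The MMRM is specified as "including fixed effects for DAS28-hsCRP baseline covariate, treatment, visit, treatment by visit interaction, and the stratification factors". Estimand 3B uses a similar model.

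So each continuous key secondary endpoint is adjusted for its own baseline, and none of the response models carries a baseline measure of activity. The text available does not name the stratification factors, does not explain the difference in approach, and leaves further detail to the SAP.

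**The concern.** At about 45 evaluable participants per arm, the interval for a difference in percentages is wide: the standard error is about 10 percentage points at the planning rates. A baseline variable that predicts response can narrow it without more participants. The obvious candidate must already be derived for the MMRM, so no new data are required. The margin over the stated power is also small. At stake is the width of the primary interval and possibly a few points of power. The validity of the primary comparison is not in question.

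**Working it through.** **1. Reproduce the plan's figure.** Inputs from the Sample Size section: 35% v 65%, two-sided 5%, 80% power, about 45 per arm (180 in total), 20% loss, 224 randomised.

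- Required n per arm (normal approximation, pooled variance under the null): [1.96 × √(2 × 0.5 × 0.5) + 0.842 × √(2 × 0.35 × 0.65)]² / 0.30² = (1.386 + 0.568)² / 0.09 = 42.4, so 43.
- Power at 45: null SE = √(0.5/45) = 0.1054; alternative SE = √(0.455/45) = 0.1006; Φ[(0.30 − 1.96 × 0.1054)/0.1006] = 82.4%. Exact enumeration of the uncorrected chi-square gives 81.3%.
- Loss: 180/0.80 = 225, against 224 stated.

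The design reaches its stated power with no covariate.

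**2. What a covariate could add.** If it explains a share R² of the within-arm outcome variance beyond the existing terms, the variance is multiplied by (1 − R²) and the effective n is 45/(1 − R²). R² is an assumption; the documents give no value.

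| Assumed R² | SE of difference | Effective n per arm | Power |
|---|---|---|---|
| 0 | 0.1006 | 45.0 | 82.4% |
| 0.02 | 0.0995 | 45.9 | 83.1% |
| 0.05 | 0.0980 | 47.4 | 84.3% |
| 0.10 | 0.0954 | 50.0 | 86.2% |
| 0.15 | 0.0927 | 52.9 | 88.1% |

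**3. Simulation of the variance ratio.** Settings: 45 per arm, 35% v 65%, logistic fit, risk difference by averaging predicted probabilities. The entries are variance with the continuous covariate divided by variance without it. In the right-hand column both models already contain a stratum that is a median split of the same measure.

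| Assumed log odds ratio per SD | No stratum captures activity | Median-split stratum in the model |
|---|---|---|
| 0 | 1.01 | 1.02 |
| 0.3 | 0.99 | 1.01 |
| 0.5 | 0.94 | 0.98 |
| 0.7 | 0.92 | 0.98 |
| 1.0 | 0.85 | 0.96 |

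Repeat runs move individual cells by a few points: the 0.5 entry in the middle column ranged from 0.94 to 0.97, and the reduction at 1.0 with a stratum was 4% to 5%. At 0.7 without a stratum, 45/0.92 = 48.9 effective participants per arm. In the worst cell, 45/1.02 = 44.1.

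**4. Does the estimand change?** A four-arm simulation (4,000 runs per setting) gave SD ratios of 1.004, 0.999, 0.984, 0.961, 0.940 and 0.919 at log odds ratios of 0, 0.2, 0.4, 0.6, 0.8 and 1.0. Squared, these are 1.01, 1.00, 0.97, 0.92, 0.88 and 0.84, in line with the middle column above. The mean difference was the same with and without the covariate (0.298 to 0.303), and type I error was 5.5% to 6.2% for both Wald tests. The standardised risk difference therefore targets the same quantity.

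**5. The dose-trend model is different.** It reports a slope for dose in mg, which is on the log-odds scale. A log odds ratio is non-collapsible: adding a prognostic covariate changes what it estimates. In a two-arm simulation at 0.7 per SD, the treatment log odds ratio moved from 1.26 to 1.42 and its SD rose from 0.46 to 0.51. The precision argument does not carry over.

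**The case against.** The strongest reply is that nothing here is wrong. Adjusting for the stratification factors is a standard pre-specified choice, it estimates Estimand 1 validly, and the stated power is met. That stands in full.

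Second, the analogy with the secondary models is weak. The MMRM and the ANCOVA analyse change on the same scale as the baseline that they adjust for. ACR20 is a percentage improvement from each participant's own baseline, and the composite also counts discontinuation for tolerability or lack of efficacy and any increase in RA medication as failure. Entry criteria narrow the range of activity (for example, "≥6 swollen joints (based on 66 joint counts) at screening and baseline visits"). The link between baseline DAS28-hsCRP and response may therefore be weak. This stands, and it is why the gain is given as a range that starts at zero.

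Third, an unnamed stratification factor may already capture disease activity. This also stands. A continuous term would still add something, but the right-hand column in step 3 shows that it would be little.

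A reader might infer that the trial is throwing away precision that is certain and free. The documents do not support that: they give no prognostic strength, and a covariate with none costs about 1% to 2% in variance. A reader might also infer that the covariate belongs in every logistic model. Step 5 shows why that fails for the dose trend.

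**Conclusion.** The omission is confirmed for Estimands 1 and 4, and adding the covariate is a reasonable low-cost improvement. It corrects no error or bias and is not needed to reach 80% power. For a log odds ratio of 0.3 to 1.0 per SD, the variance of the difference in percentages falls by about 0% to 15% if no stratum captures activity, and by about 0% to 5% if one does. By the formula in step 2, a 5% reduction corresponds to power of 84.3% and a 15% reduction to 88.1%, from 82.4%. The only downside found is a variance increase of about 1% to 2% if the covariate is not prognostic.

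These sizes rest on three assumptions that the documents cannot settle: the prognostic strength, whether a stratum already reflects activity (represented here by a median split), and a single, roughly normal covariate acting linearly on the log-odds scale.

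**What to change.** - Name the stratification factors where the primary model is described.
- Pre-specify continuous baseline DAS28-hsCRP as a covariate in the Estimand 1 and Estimand 4 logistic models and in their multiple-imputation versions. State how a missing baseline value is handled.
- State how the fitted model becomes a difference in percentages: average each participant's predicted probability under each dose and under placebo, take the difference, and use the delta method for its SE.
- Keep the present model, with treatment and strata only, as a sensitivity analysis.
- Leave the dose-trend logistic model unchanged.

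The cost is a few lines of analysis-plan text and one model degree of freedom. No new data, visits or participants are needed. The change should be fixed before unblinding so that the choice of covariate cannot depend on the results.

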MBS2320 is being developed for the once daily oral therapy of RA. Based on the non-clinical and clinical data generated to date, it is anticipated that MBS2320 can have a direct impact on structural damage in RA, in contrast to the current standard of care, and a reduced propensity for adverse events (AEs) arising from immunosuppression.

Objectives and Estimands:

Objectives

Primary Objective

To evaluate the efficacy of MBS2320 (5 mg once daily, 20 mg once daily, and 40 mg once daily) compared with placebo in participants with active RA on stable background MTX who have had an inadequate response to MTX alone, with confirmed intra-articular synovitis on baseline MRI.

Estimand Description (Including Endpoint)

Primary Endpoint: Composite clinical response (Success/Failure) at Week 12 defined as:

- Achieving clinical response according to the criteria for ACR20:
 - $\circ \geq 20\%$ improvement in 68-TJC;
 - $\circ \geq 20\%$ improvement in 66-SJC; and
 - ≥20% improvement in at least 3 of the 5 following parameters:
 - Physician's global assessment of disease activity
 - Participant's global assessment of disease activity
 - Participant's assessment of arthritis pain
 - HAQ-DI

Objectives

Estimand Description (Including Endpoint)

- hsCRP
- Not discontinuing treatment due to tolerability issues or lack of efficacy; and
- Not requiring any increase in RA medications either in background medication dose (MTX) or any further alternative RA treatment or procedure.

Primary Estimand 1: Difference in percentage of patients with moderate to severe active RA and a previous inadequate response to MTX alone, with confirmed intra-articular synovitis on baseline MRI, who would have a successful composite clinical response after 12 weeks of treatment with MBS2320 (5 mg, 20 mg, or 40 mg once daily) compared to placebo (each on top of stable background RA medication of weekly MTX). A successful composite clinical response is defined as achieving clinical response according to the criteria for ACR20 without discontinuing treatment due to tolerability issues or lack of efficacy or requiring any increase in RA medications, but irrespective of any interruptions required for treatment related reasons.

Endpoint: Change in RAMRIS scores (synovitis, bone oedema, and bone erosion scores, measured with MRI) from baseline to Week 12.

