A blood sample for pharmacogenomics analysis will be taken on Day 1.

Details of Applicable Monitoring Committee:

Not applicable.

Investigational Product, Dosage, and Route of Administration:

The IP will be presented in a capsule formulation containing immediate release powder of active drug (MBS2320) or placebo. All capsules will be identical in size and colour (opaque white) and contain MBS2320 at unit doses of 5 mg, 20 mg, or 40 mg, or placebo. The excipients used in MBS2320 comprise standard compendial pharmaceutical excipients: sorbitol, sodium lauryl sulphate, and magnesium stearate. On each dosing occasion, participants will swallow 1 capsule whole with food and a glass of water (approximately 250 mL). Participants will be instructed to contact the Investigator in case they experience emesis after dosing. Any episode of emesis after dosing will be reported as an AE and is to be managed with anti-emetics, as advised by the Investigator. The IP dose should not be repeated if emesis occurs after dosing and the participant should be instructed to take the IP at the next regularly scheduled time.

Sample Size:

This study has been powered assuming that 180 participants (approximately 45 per treatment arm) with confirmed IA synovitis at baseline provide an ACR20 composite clinical endpoint at Week 12; this would provide 80% power to detect a difference between placebo (assuming 35% response) versus MBS2320 (assuming 65% response) using a two-sided 5% significance level. Thus, it is anticipated that approximately 224 participants will be randomized which allows for a loss of 20% which may be due to unconfirmed IA synovitis, treatment discontinuation due to reasons unrelated to tolerability or worsening disease or for an unknown reason (loss to follow up without prior related intercurrent events). Note that participants who either discontinue treatment due to tolerability issues or require further treatment or increases in RA medication due to worsening disease do provide an ACR20 composite clinical endpoint (treatment failure) even if they do not provide study data at Week 12.

Statistical Methods:

The following analysis sets will be used in the statistical analyses.

Enrolled Set The enrolled set will consist of all participants who sign the ICF.

Safety Set

The safety set will consist of all participants who receive at least 1 dose of MBS2320 or placebo. All analyses using the safety set will

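### For Estimands 1 and 4, the already planned multiple imputation under MAR is a better main estimator than complete-case analysis under MCAR, though the expected gain is modest

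*Combined protocol and SAP*

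**What the plan says.** All references are to the protocol synopsis.

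- **Endpoint (Objectives and Estimands, Primary Endpoint).** Success has three elements: ACR20 response; no step-up in RA therapy, whether a higher MTX dose or another RA treatment or procedure; and, as to discontinuation, "Not discontinuing treatment due to tolerability issues or lack of efficacy".
- **Failure rule (Sample Size).** Participants with tolerability discontinuation, or with added RA treatment for worsening disease, "do provide an ACR20 composite clinical endpoint (treatment failure) even if they do not provide study data at Week 12". The main estimation text for Estimand 1 applies the same rule and names lack-of-efficacy discontinuation as well.
- **What can be missing (Sample Size; Modified Full Analysis Set, Flag P).** Unrelated discontinuation, or "loss to follow up without prior related intercurrent events". Flag P "Censors data after discontinuation or interruption of treatment for unrelated reasons". The sample size "allows for a loss of 20% which may be due to unconfirmed IA synovitis" among other causes, but the split between causes is not given.
- **Main estimator.** For Estimand 1: "Missing data will not be imputed and are assumed missing completely at random (MCAR". The main estimation text for Estimand 4 says the same.
- **Sensitivity analyses.** Multiple imputation (MI) under MAR for Estimand 1, MI for Estimand 4 with no missingness assumption named, and a logistic mixed model over Weeks 4, 8 and 12.
- **Other estimands.** MI under MAR is the main estimator for Estimand 2A and covers censored as well as missing scores. An MMRM under MAR, with baseline DAS28-hsCRP as covariate, is the main estimator for Estimand 3A.
- **Detail.** "Details of the statistical analyses, methods, and data conventions will be described in the statistical analysis plan (SAP".

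**The concern.** A participant who fails early through a related event has a known outcome whatever happens later. A participant who would have succeeded has a known outcome only if the visit data exist. When some participants are lost, related failures are therefore over-represented among those with an outcome, and each arm's response rate is pulled down. If the arms are pulled down by different amounts, the treatment difference shifts. This happens even if the loss itself is purely random, because the composite's missingness still depends on its value.

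The main estimate also makes no use of Week 4 and Week 8 data from participants who are lost later. What is at stake is the primary estimate for each dose, and whether it rests on the least suitable of the analyses already planned.

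**Working it through.** **1. The plan's own figures.** Inputs from Sample Size: 35% v 65%, two-sided 5%, 80% power, 45 per arm, 224 randomised, 20% loss.

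- n per arm = [1.96·√(2·0.5·0.5) + 0.8416·√(2·0.35·0.65)]² / 0.30² = 42.4, so 43, against 45 stated. Power at 45 per arm is 82.4% by the same formula.
- 180/0.80 = 225, against 224 stated.
- Standard error of the difference at 45 per arm = √(2·0.35·0.65/45) = 10.1 points.

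The sample size is sound, and nothing below changes it.

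**2. Assumed inputs.** Let f be the share of an arm with a related failure by Week 12, and q the share whose outcome is lost. The documents give neither. The 20% allowance also covers unconfirmed synovitis:

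- 10% unconfirmed leaves q = 1 − 180/(224·0.90) = 10.7%
- 5% unconfirmed leaves q = 15.4%
- none unconfirmed leaves q = 1 − 180/224 = 19.6%, the ceiling

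I use q = 10%, equal in both arms, with 20% as the ceiling.

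**3. Complete-case response rate** for true rate r, with loss independent of outcome:

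- Data missing only at the Week 12 visit: r(1−q) / [(1−f)(1−q) + f].
- Loss spread evenly over 12 weeks: r(1−q) / [(1−f)(1−q) + E], where E = λ/(λ+μ)·[1 − (1−f)(1−q)], λ = −ln(1−f), μ = −ln(1−q).

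Example with f = 20% in both arms and q = 10%. Week 12 only: 0.315/0.92 = 34.2% and 0.585/0.92 = 63.6%, a difference of 29.3. Even loss: E = 0.190, so 0.315/0.910 = 34.6% and 0.585/0.910 = 64.3%, a difference of 29.7.

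Complete-case difference in points, true value 30, q = 10%:

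| f placebo/active | Even loss | Week 12 only |
|---|---|---|
| 10/10 | 29.8 | 29.7 |
| 20/20 | 29.7 | 29.3 |
| 15/10 | 29.9 | 29.9 |
| 20/10 | 30.0 | 30.0 |
| 10/15 | 29.7 | 29.3 |
| 15/20 | 29.6 | 29.2 |
| 10/30 | 29.1 | 28.3 |
| 30/10 | 30.2 | 30.4 |

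The bias is about 0 to -0.7 points for similar shares (-0.8 at 15/20), and -1.7 to +0.4 for the two extreme splits. At q = 20% the extreme splits give 26.3 to 30.9.

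If f is instead an equal share of the non-responders in each arm, with equal loss, the bias is 0 to -0.1 points.

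**4. Unequal loss.** With f = 20/20 and q = 10% placebo, 20% active, the difference is 28.8 (even loss) or 27.7 (Week 12 only).

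**5. Estimand 4**, reusing 35%/65%, even loss, with f and q scaled to the visit. For 20/20, 10/30 and 30/10: Week 4 gives 30.0, 29.9, 30.0; Week 8 gives 29.9, 29.6, 30.1.

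**6. Imputation under MAR**, q = 10%, even loss, same three cases:

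- All three elements imputed (simulation, 6 million per arm): 30.0, 29.9, 30.0.
- ACR items only: 30.4, 31.1, 29.6. With data missing only at Week 12 this version is unbiased.

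Simulated power at 50 per arm was 82.9, 81.4 and 84.1% for complete-case, against 83.8% for imputing all three elements: a change of -0.3 to +2.4 points, with Monte Carlo error of about 0.5. It assumed Week 4 and 8 ACR20 rates at 60% and 85% of the Week 12 rate, and a latent correlation of 0.7 between adjacent visits.

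**7. Loss not at random.** If 10% are missing in both arms and all are failures, the difference is 58.5 − 31.5 = 27.0. If only the active arm has missing data, it is 58.5 − 35 = 23.5.

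**8. Baseline covariate.** Large-sample variance reduction = [ρ·φ(z₀.₆₅)]² / (0.35·0.65), with φ = 0.370: 2.4% at ρ = 0.2 and 9.6% at ρ = 0.4. Simulation at 45 per arm gave 1.2% and 8.5%, and a loss of 1.0% at ρ = 0. The documents do not give ρ.

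**The case against.** The strongest reply is that the plan already covers this. Related failures are counted, MI and a logistic mixed model are planned, and both use the earlier visits. On this view the point only swaps the labels main and sensitivity. That is largely fair, but the choice still fixes which number is the primary result.

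A reader might infer that the plan contradicts itself or drops known failures. It does neither. The Sample Size and main estimation texts agree on who fails, and MCAR is applied only to what remains, a loss process that could itself be random.

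A reader might also infer a material bias in the primary result. The documents do not support that. The larger figures need a 10%/30% split of related failures, which would mean 65/70 = 93% of active participants without a related failure reach ACR20, against 35/90 = 39% on placebo. Nothing in the documents suggests this. The 20% ceiling further requires that nobody is lost to unconfirmed synovitis.

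Two more objections stand in part. Estimand 2A is hypothetical and censors data after every intercurrent event, so imputation matters more there than here. Imputing non-ACR elements is a tailored step that rests on about 5 to 15 events per arm at f = 10% to 30% of 50.

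The scope of the planned MI is a matter of detail that the protocol leaves to the SAP. The natural reading of the text covers all three elements, and this would not be a point on its own.

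**Conclusion.** The point holds as a better choice of main estimator, not as an error in the plan's figures. If related failures and outcome loss both occur, MCAR for the composite will not hold in general.

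Under the assumed 10% loss, equal in both arms, the resulting bias is a fraction of a point in the more plausible cases. It is at most about 1.7 points in the extreme ones, roughly 0.2 of a standard error. For Estimand 4 it is smaller still. Unequal loss can add to it.

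All of this depends on assumed f and q and on loss unrelated to the unseen outcome. Loss not at random could matter more, and neither estimator corrects it. The case for change is consistency with the failure rule, use of data already collected, and low cost.

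**What to change.** In the SAP, before unblinding:

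1. Make MI under MAR with Rubin's rules the main estimator for Estimands 1 and 4. Name the MAR assumption for Estimand 4 too.
2. Hold known related failures as failures, and use Week 4 and 8 data in the imputation model.
3. Apply the imputation to Flag P-censored values as well as missing ones, and to all three elements of the composite.
4. Keep the complete-case analysis as a sensitivity analysis.
5. Separately, add baseline DAS28-hsCRP to the logistic model and report the standardised difference in percentages.

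The cost is wording only, with no new data, visits or participants. The imputation model, number of imputations and seed must be fixed in advance. Imputation of the non-ACR elements rests on few events per arm. The covariate could cost about 1% in variance if it is unrelated to response. A tipping-point analysis would be a useful optional addition, since loss not at random remains.
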